In order to address the fourth question above concerning the prescribing content (medicines management) of TPP versus SFH contracts, a qualitative study may be undertaken to investigate whether TPP practices and SFH practices differ in the details on prescribing issues which are written into contracts. Whether this study goes ahead will depend whether changes are negotiated informally by TPPs or made explicit in contracts. It may be possible to establish this through telephone interviews before deciding whether to

invest additional resources in this area. If it goes ahead, this study would also attempt to ascertain whether any differences are greater as the level of prescribing budgets per patients becomes lower. The analysis would concentrate initially on three areas: patients discharged from A&E; early discharge from surgical wards; and, day case surgery. In each area, the requirements in contracts concerning the drugs to be provided to patients would be described.

The same 24 practices used in the DDD analysis of psychotropic drug use would be used for this study. Structured CATIs would be conducted with lead GPs and those involved in contract negotiations in mid-1996, autumn 1996 and early 1997. This work would be informed by the general analysis of the content of contracts carried out by IHPS, Southampton as part of the 'core' evaluation.

6: TRANSACTIONS COSTS OF TOTAL PURCHASING

Lead: [name], NPCRDC at York

Main comparison: Detailed costs at a small number of TPP sites versus matched sample of

districts without TPPs

Introduction

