The study will focus on the *incremental* costs associated with the change from Model 2 to Model 3, and will consider costs falling on all of the main affected parties: GPs, the DHA/FHSA; and the main acute, community and mental health providers. The way in which the comparison has been framed means that it is not possible to restrict attention solely to the transaction costs borne by general practitioners.

Specific questions

Within the budget set for the study, the extent of comparative information which can be collected is limited. However, it should be possible to address a number of key research questions.

1. What differences exist, if any, in the transaction costs associated with different TP sites? What seem to be the ways of minimising transaction costs?

Some information will be available from the first phase of the 'core' evaluation (involving all sites in England and Scotland - see section 4) to allow a broad taxonomy to be developed of different ways of organising total purchasing, and of differences between sites in terms of level of activity. A comparison of the costs associated with different sites drawn from the taxonomy should provide some insight into the main determinants of differences in cost.

The core evaluation will also provide some limited information on transaction costs for all sites which will strengthen this aspect of the comparison.

2. What are the likely costs to primary care providers (general practice teams) involved in a move from standard fundholding to total purchasing?

This question can be addressed in two ways: i) by means of a before-and-after comparison of pilot sites within the study which were previously standard fundholders; and ii) by a comparison of costs in the TPP site with those in a matched SFH control practice (or group of practices) within the same DHA.

3. What are the additional costs (to GPs, DHA/FHSA and local providers) resulting from the introduction of total purchasing alongside DHA and SFH purchasers?

As a minimum, this question can be addressed by a before-and-after comparison of costs to the DHA/FHSA, GPs themselves and the main local providers. For the DHA/FHSA and providers, a before-and-after design may not be necessary, since they will be dealing currently with both SFHs and TPPs. In this case it should be possible to isolate incremental costs directly.

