If resources are sufficient, it would also be useful to compare the costs to DHA/FHSA and providers in a TPP District with costs in a comparable District without a TPP. This would be a useful control against the possibility that Districts with TPP sites are in some way unrepresentative of Districts as a whole.

To facilitate comparison, the magnitude of transaction costs will be expressed initially as a percentage of total health expenditures. The study will, however, offer an opportunity to test the viability of other possible units of comparison.

Method

Apart from the work of Bevan (1995a, b), which is set very much at a macro level, and one unpublished study commissioned by the NHS Executive, there are no previous studies in the UK which attempt to estimate transaction costs in the NHS (or in health care more generally. See Pitelis (ed), 1993). Developing and testing a suitable methodology is therefore an important objective of this study.

With the exception of the limited amount of information which will be collected as part of the core evaluation covering all of the TPP sites, all of the information relevant to this study will be collected from a sample of sites drawn from the national pilots. Details of the principles of sample selection are outlined below.

Transaction costs arise from functions or activities associated with the need to obtain information, and the need to negotiate, monitor and enforce contracts. The main part of the study will involve a series of semi-structured interviews with key stakeholders in each of the organisations identified above: the TP manager and lead GP in the TPP site; the DHA/FHSA lead; the lead GP in a control SFH practice locally; and representatives of each main local provider (typically the main acute, community and mental health Trusts).

The objective of the interviews will be to identify:

- 1. the range of additional functions or activities associated with total purchasing, and
- 2. the *resources* (in terms of personnel, time and other resources) which are devoted to undertaking these activities and functions.

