Information will be collated and analysed within a structure such as that shown in Figure 6.2, which will also form the basis of a questionnaire to be used in the interviews. In Figure 6.2 the main potential sources of transaction costs are classified into four groups: i) the costs of information; ii) contract-related costs; iii) costs which are activity-related; and iv) the costs associated with coordinating activity within the TPP group and between the TPP and the DHA/FHSA. This is a generalisation of the main sources of transaction costs identified above.

It is in the nature of the questions which need to be addressed in this part of the work that most of the relevant information (for example, about functions and activities) will be qualitative. This will be supplemented with quantitative data on resource use and costs.

Further contact with the TPP site, the DHA/FHSA lead and the main provider organisations will seek to identify:

 the costs of the real resources associated with functions, and with the time and personnel inputs identified in the interview.

It is expected that each site will be visited at least twice: once in each of the two contracting years of the study. Data will be analysed in line with the research questions outlined above.

The use of a diary card in the periods between interviews to record the use of time will be considered. This is a feature of the design of the core evaluation which may usefully be adapted for use in the present study.

In addition, it is intended to attempt a broader (macro) approach to estimating transaction costs by comparing total health expenditure in the sample Districts with some global measure of activity (such as FCEs) in each of the sample years and in the preceding year. Although crude, some global measure of NHS expenditure per FCE (or incremental FCE per £000 of additional budget in each year) will give an indication of the extent to which additional spending is associated with additional activity or additional administration costs

Sample Selection

The size of sample which can be handled within the study is a function of the extent of resources available. The design suggests the need to carry out 6-7 interviews per year for each pilot site included in the sample: even more if a comparison is attempted with a non-TPP District. The need to collect additional cost information will increase the number of potential contacts by a further 50 per cent.

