With the equivalent of one half-time research fellow assigned to the project, the number of sample sites must be limited to four. The alternative is to reduce the number or intensity of contacts at each site, but this is not a strategy which is consistent with our aims of undertaking a thorough analysis and of testing a new methodology.

Each of the four selected sites will be visited twice: once in each year of the study. Additional visits will be required to collect cost data and (undoubtedly) to respond to requests to feedback information to participants. In the second year, if resources are available, it is also intended to include interviews with DHA/FHSA and provider representatives (around 3-4) in four non-TPP control Districts.

On the basis of information collected as part of the core evaluation (see section 4), it should be possible to construct a taxonomy of different ways of organising total purchasing (for example, different ways of coordinating participating practices, or different means of communication between the DHA/FHSA and the TP pilot) which are expected to be of relevance to the level of transaction costs. The sample of sites will be selected as far as possible to be representative of this taxonomy.

FIGURE 6.1 MODELS OF PURCHASING

		Model 1 DHA		Model 2 DHA +SFH	DHA	Mod +SFI		TPP
DHA/FHSA	х		х		х			х
GPTP							x	x
SFH				x		x		
PROVIDER	x		x	x	x	x	x	

FIGURE 6.2 TRANSACTIONS COSTS - BY SOURCE OF COST

SOU	JRCES OF COST	PROCESS AND ACTIVITY	PERSONNEL AND TIME	OTHER RESOURCES (SUCH AS I.T.)
	INFORMATION			
1.	Needs/demand forecast	* +	TO BE	TO BE
2.	HC supply	*	IDENTIFIED	IDENTIFIED
3.	Competitors	+		
4.	Purchaser plans	+		
5.	Risk assessment	* +		
СО	NTRACT-RELATED			
-	C .: C:	*	"	"
5.	Specifying contracts	* +		
6.	Negotiations	*		
7.	Monitoring	**		
8.	Enforcement	-		
	Advertising/marketing	+		
	Contract pricing	+		
	Contract compliance	+		
12.	Risk sharing	* +		
AC	TIVITY-RELATED			
13	Admitting	+	دد	"
	Billing	+		
	Claims processing	*		
	Management information			
10	systems	+		
C	O-ORDINATION/OTHER			
	Grand Table 1	*	"	44
	Strategic planning	+		
18	Business planning		.	
	Resource allocation	€		
	Budget setting	€	,	
21	-	_		
	ordination	€		
	2. Liaison	€		
	Surplus sharing	€		
24	1. Protocols)	

^{*=} purchaser += provider ⊕= group

7: IMPACT ON PATTERN AND COST OF CARE AND PATIENTS' EXPERIENCES OF SPECIFIC SERVICES

7.1: RATIONALE FOR STUDIES OF SPECIFIC SERVICES AND GROUPS OF PATIENTS

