Transactions costs (6)	See below	[name] (lead, NPCRDC at York) [name] (Soton) [name]	
Direct (basic) administrative costs/transactions costs (4)	All TPP sites as in 4, above		April 1995 - March 1997
Indirect (detailed) transactions costs	Sample of TPP sites and DHAs without TPPs, to be decided		August 1995 - March 1997
Patients attending A&E and emergency admissions (7.2)	No of A&E depts to be decided based on feasibility study to compare patients of TPPs and local SFHs	[name] (lead,LSHTM) [name] (KFI)	April 1996 - March 1997
Service provision, outcomes and costs for seriously mentally ill people (7.3)	See below	[name] (lead, NPCRDC at Manchester)	
Work of CPNs	Sample of TPP sites and SFH practices		April 1996 - March 1997
Strategic approaches and services for mental health services	All TPP sites and local health authorities (as in 4, above)		April 1995 - June 1997
Outcomes for severely mentally ill people	Sample of TPP sites and SFH practices sufficient to yield 50 patients from each		April 1996 - March 1997
Costs of mental health services	Sample of TPP sites and SFH practices	[name] (lead, KFI)	September 1995 - July 1997

Service provision, outcomes and costs for people with complex needs for community care services (7.4)	Small number of TPP sites with/without a special interest and SFH practices (total c.8)	[name] (lead, NPCRDC, Salford)	August-December 1996
Costs of community care services	Small number of TPP sites and SFH practices (total c.9)	[name] (lead, KFI)	September 1995 - July 1997
Users of maternity services (7.5)	See below	[name] (lead, Edin)	
Pattern of maternity care purchased	All TPP sites and local HCs		April 1995 - March 1997
Users' experiences of maternity services	Sample of TPP sites and local HCs		April 1995 - June 1997
Costs of maternity services	All TPP sites and local HCs		September 1995 - July 1997

For the remaining components of the evaluation (in Table 8.1), a specific centre and individuals within each centre will be responsible for design, analysis and reporting. However, the fieldwork and data collection will not necessarily all be undertaken from the lead centre. Thus, whereas it is the intention that all the data collection on A&E (section 7.2) will be undertaken by LSHTM, the detailed data collection on service costs and efficiency (section 5.2) will be shared between the collaborating centres with the design, analysis and reporting undertaken by King's Fund Institute staff.

PROJECT MANAGEMENT

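### The transactions-cost component names districts without TPPs as its main comparator, but its method makes them optional and commits to no non-TPP series for the expenditure-per-FCE measure

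*Protocol*

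**What the plan says.** All references are to the protocol.

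- **Section 6, Main comparison line:** "Detailed costs at a small number of TPP sites versus matched sample of", continued on the next line as "districts without TPPs".
- **Table 8.1, detailed transactions costs:** "Sample of TPP sites and DHAs without TPPs, to be decided", with data collection from August 1995 to March 1997. Table 3.1 marks the comparison with districts without TP for transactions costs with an asterisk, not with the question mark it uses for comparisons that look difficult.
- **Section 6, Models of Purchasing:** the target is the incremental "costs associated with the change from Model 2 to Model 3, and will consider costs falling on all of the main affected parties". Those parties are GPs, the DHA/FHSA and the main providers. Model 2 is DHA plus standard fundholding (SFH); Model 3 adds TPPs.
- **Section 6, Specific questions (question 3):** before-and-after is the minimum. For the DHA/FHSA and providers even that may be dispensed with, because they deal with SFHs and TPPs at the same time and the extra cost might be isolated directly. The non-TPP district then appears as an extra: "If resources are sufficient, it would also be useful to compare the costs to DHA/FHSA and providers in a TPP District". Its stated purpose is to check whether TPP districts are typical.
- **Section 6, Method:** apart from core-evaluation data, all information comes from a sample of the national pilots. A macro estimate is also planned, by "comparing total health expenditure in the sample Districts with some global measure of activity (such as FCEs"), for each sample year and the year before.
- **Section 6, Sample Selection:** a half-time research fellow limits the sample to four sites, each visited once in each of two years. Then: "In the second year, if resources are available, it is also intended to include interviews with DHA/FHSA and provider representatives". The number of such interviews is put at about three or four, and the control districts, four of them, would have no TPP.

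**The concern.** The header and Table 8.1 promise a contrast that the method makes conditional on money. The choice of comparator matters because a concurrent Model 2 exists only where there is no TPP. The local SFH control practice works under the same DHA and with the same trusts as the TPP site. It can therefore inform the cost to GPs, but not the cost to the health authority or the providers.

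The macro measure is the most exposed part. Section 3 warns that purchasing and primary care are changing across the NHS during the evaluation, and that caution is needed even with a controlled before-and-after design. Section 5.1 lists growth in the number of FCEs per admission among the problems of routine data. A change in expenditure per FCE, seen only in TPP districts, mixes these influences with any effect of total purchasing. At stake is what may be concluded about the incremental cost of total purchasing, and whether the stated main comparison describes the evidence that will exist.

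**Working it through.** No power or formal sample size is stated, so the check is a count of what is committed.

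**Step 1. Reproduce the plan's own figure.** The Method lists the respondents per site: TP manager 1 + lead GP 1 + DHA/FHSA lead 1 + lead GP of a local SFH control practice 1 + main providers 3 (acute, community, mental health) = 7, or 6 if one trust fills two provider roles. This matches the 6-7 interviews per site per year in Sample Selection.

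**Step 2. Committed interviews.** Sites × interviews × years: 4 × 6 × 2 = 48 to 4 × 7 × 2 = 56. In non-TPP districts: 0.

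**Step 3. Optional interviews.** Reading the 3-4 as per district (DHA/FHSA 1 + providers 2-3), 4 × 3 = 12 to 4 × 4 = 16. All fall in year two. The per-district reading is an assumption, since the sentence does not say; a total of 3-4 would be at most one per district. On either reading the year-one count is 0, whether or not the option is funded.

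**Step 4. What each cost has as its contrast.**

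| Cost | Committed | Non-TPP district control |
|---|---|---|
| GPs | Before-and-after; SFH practice in the same DHA | None, even if the option is funded (no GP respondents) |
| DHA/FHSA | Before-and-after and/or direct identification of TP-related costs | None committed; one cross-section in year two if funded |
| Providers | As for DHA/FHSA | As for DHA/FHSA |
| Expenditure per FCE | Preceding year + 2 study years = 3 annual points | No series committed |

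**Step 5. What the macro measure can show.** Within TPP districts, change in expenditure per FCE = TP component + NHS-wide component + recording component. One set of districts cannot split this sum. With a matched non-TPP series over the same years, (change in TPP districts) − (change in non-TPP districts) removes what the two sets share. It does not remove recording changes peculiar to one provider, which section 5.1 shows are possible when it describes units that record similar admissions differently. It also does not undo the dilution that arises because a TPP covers only part of its district.

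**The case against.** The strongest reply is that section 6 does not depend on a non-TPP control for its detailed estimates. The interviews aim to itemise the functions that total purchasing adds and the resources they use. A DHA or trust dealing with both SFHs and TPPs is well placed to identify that increment directly, so sharing the DHA is an advantage for this purpose. The optional districts are offered as a check on representativeness, which one cross-section can serve. Section 6 also makes steady-state costs the primary interest, which favours a second-year look. The resource limit is disclosed in sections 3 and 6, section 4 calls contracting interviews in control districts likely, and the macro measure is itself called crude.

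Most of this stands, and it rules out some stronger readings. A reader might infer that every change in DHA and provider management cost would be credited to total purchasing with the national trend left in. The protocol does not support that, because it plans to identify TP-related costs, not to difference total management cost. A reader might also infer that the missing comparison would be reported as if it had been made; nothing in the protocol says so. Nor can the bias in the macro measure be sized: the protocol gives no TPP share of a district's population, and the coverage figures in the A&E study were assumed only to time the collection of attenders.

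It might also be said that the sample districts in the macro paragraph include non-TPP districts, since Table 8.1 lists them. That reading is open, but those districts enter only if resources allow, so no control series is committed either way. Disclosing a condition also does not make it consistent to call the conditional arm the main comparison.

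**Conclusion.** The inconsistency is in the text and should be corrected. The stated main comparison has no committed control districts: 0 of 4, with no observations in year one under any scenario and at most one cross-section in year two. What is committed is two visits at four TPP sites, with before-and-after and/or direct identification of incremental costs, and a same-DHA SFH control for GP-side costs only.

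Two limits on interpretation follow. DHA/FHSA and provider costs rest on respondents' attribution within TPP districts. Expenditure per FCE, as planned, cannot distinguish total purchasing from NHS-wide trend or changed FCE recording.

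This does not invalidate the component. It narrows what can be concluded, and the macro part can be improved cheaply. The finding rests on the wording of the header, Table 8.1, Specific questions, Method and Sample Selection, and on no assumed effect size or trend.

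**What to change.** 1. **Add a control series to the macro measure.** Once the four TPP sites have been selected, and not before, because the controls must match them, choose matched non-TPP districts. Compute expenditure per FCE for them from the same routine returns and for the same preceding and study years. Report the difference in change between the two sets, still labelled crude, because any effect is diluted at district level and local recording changes may not cancel. With four control districts this means 4 × 3 = 12 further district-year figures. The cost is obtaining those routine data; no interviews are needed.
2. **Make the header and Table 8.1 match the method.** State the main comparison as before-and-after and/or direct identification of TP-related costs at four TPP sites, with a same-DHA SFH control for GP costs only. List non-TPP district interviews as a secondary, cross-sectional, resource-dependent check on representativeness. The cost is rewording, and a more modest stated comparison.
3. **State the limit on DHA/FHSA and provider costs.** Say that these estimates depend on respondents' attribution within TPP districts and have no external control unless the optional interviews take place. This costs one sentence.

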1. HISTORY OF THE SITE

Were the practices previously involved with one another? If so, in what way (e.g. locality purchasing, SFH consortium, etc)?

What role did the health authority/health commission play in identifying and recruiting the site?

When was the site officially confirmed and when did it begin its preparation?

What was the extent of discussion and interaction between the practices and the individual GPs?

2. AIMS AND OBJECTIVES

What are the aims (general philosophy and motives) of the site for TP?

What are the site's objectives in relation to each service area in TP in the first year of the scheme with particular reference to services which will be the subject of specific study?

These services are: A&E/Emergency (*); Mental Health (*), Community Care (*), Continuing Care/People with Complex Needs (*); Maternity (*); Palliative Care; Regional Specialities; and Health Promotion of which the services marked with a (*) are subject to further study as components of the evaluation.

Include details of changes to any of these services which the site wishes to make in year one.

Are there any new objectives for subsequent years?

How would the site assess whether or not its objectives had been realised?

What are the main local and national enabling and retarding factors for success as perceived by the respondent?

